### **One-On-One Data Collection Interview**

Study staff will interview participants at the housing facility to obtain contact and socio-demographic information and enter participant responses to the Participant Questionnaire which includes medical history, oral health behavior, oral health symptoms, tooth pain/sensitivity, and oral health quality of life.

### **Baseline Dental Exam**

- Dentists will administer the Safety Questionnaire (Pre-Exam).
- Hygienists will perform initial dental exam examination at participant's respective housing facility to determine eligibility to continue in the clinical trial based on caries status.
- Study staff will record results of dental exam examination.
- Hygienists, under the direction of the study dentist, will proceed as follows:
- If the participant has an urgent cavity or another serious dental problem, they will be instructed to go for dental care immediately and their participation will end.
- If the participant has no cavities or other urgent problems, they will be instructed to continue regular visits with their dentist and their participation will end.
- If the participant has cavities that require treatment but no urgent problems, they will receive one of two treatments at this visit and will continue to participate in the research. Hygienists will administer the intervention treatment (based on study arm) to all untreated active root or coronal carious lesion with ICDAS-II lesion severity code of 3 or greater.
- If a participant reports any issue with the applied treatment within one week of the treatment date, the study team will return to the housing facility to examine and correct the treated tooth as needed. Within 48 hours, the study team will call the participant to ask the participant if the issue has been resolved and will administer a paper safety questionnaire. The completed paper safety questionnaire will be stored in the CRF folder and documentation of the return visit/treatment will be added to the participant's electronic record.

### **Follow-Up Data Collection**

- Study staff will contact participants who received treatment by phone (within 48 hours of treatment) to complete the safety survey.

## **7.2 26-Week Visit (T26) (Day 168 to Day 196)**

### **Dental Exam and Treatment**

- Dentists will administer the Safety Questionnaire (Pre-Exam).

- Hygienists will perform dental examination at participant's respective housing facility to evaluate caries arrest and identify new decay.
- Study staff will record results of dental examination.
- Hygienists, under the direction of the study dentist, will administer the intervention treatment (based on study arm) for all previously treated lesions and newly identified active root or coronal carious lesion with ICDAS-II lesion severity code of 3 or greater.
- Study staff will give participants referral sheets with exam results and direction to follow up with their personal dentist for routine dental care.
- If a participant reports any issue with the applied treatment within one week of the treatment date, the study team will return to the housing facility to examine and correct the treated tooth as needed. Within 48 hours, the study team will call the participant to ask the participant if the issue has been resolved and will administer a paper safety questionnaire. The completed paper safety questionnaire will be stored in the CRF folder and documentation of the return visit/treatment will be added to the participant's electronic record.

### **Follow-Up Data Collection**

- Study staff will contact participants by phone (within 48 hours of treatment) to complete the safety survey.
- Study staff will interview participants one-on-one at the housing facility to update contact information and enter participant responses to the oral health symptoms, tooth pain/sensitivity, and oral health quality of life and satisfaction surveys.
- Study staff will randomly select 24-30 participants who have completed treatment for three focus group sessions to be held at a housing facility during years two and three. Participants will be selected from those who have completed treatment and is geared to understanding participant experiences with non-surgical regimens and to identify ways to improve and disseminate in other community-based settings nationally.

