#### 3.2 Study Outcome Measures

##### 3.2.1 Primary Outcome Measures

Primary outcomes are: (1) participant reported outcomes including tooth pain and hypersensitivity, and (2) clinical outcomes (caries arrest). Clinical outcomes will be assessed through dental exams conducted by calibrated examiners. Participant questionnaire will assess patient-reported outcomes using validated instruments. All primary outcomes will be measured at baseline, 26 & 52 weeks.

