### 5.4.2 Masking Procedures (IR-6)

We will attempt blinding of participants to the study group, but this may not be possible due to SDF color change.

The hygienists will be unaware of the treatment assignment when they go to their respective housing facilities. For all treatment visits, assessments will be conducted prior to the intervention delivery.

Two hygienists will go to the housing facility randomized to the SDF arm and the other two will go to the ART + FV arm. The baseline treatment to be applied will be revealed only after the baseline caries exam has been completed. At the 6 month follow-up visit, the two hygienists that applied SDF will now go to the facilities randomized to the ART + FV facilities and vice-versa to conduct the 6-month follow up caries assessment exam and treatment. We will follow similarly for the 12-month follow-up visit. By this strategy, we will make sure that potential bias of the hygienist evaluating their own work is minimized. Additionally, periodically we will check for the quality of the assessment data by [name] randomly examining 20% of the participants.

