## **APPENDICES**

### **APPENDIX A: SCHEDULE OF EVENTS**

## APPENDIX A: SCHEDULE OF EVENTS

Measure/Process	Type	Instrument/Evaluation/Procedure	Timeline (Study Week)						
			-2	0	2	26	28	52	54
Screening and Eligibility Form	Screening and Eligibility	Screening and Eligibility Form	X						
Consent Form	Consent	Case IRB Template	X						
Consent Doc.	Consent	Case IRB Template	X						
Contact Form	Contact	Contact Information Form	X			X			
Participant Questionnaire A	Demographics	Demographics [Adapted from NHANES III] 	X						
Participant Questionnaire A	Medical History	Common Chronic Heath Condition for Adults 65+ [Adapted from NCOA 2017] 	X						
Participant Questionnaire A	Oral Behavior	Oral Hygiene [Adapted from Kuusela 1997, WHO survey 1997] 	X						
Participant Questionnaire A	Oral Health Symptoms	Self-Reported Measures of Current Oral Disease/Tissue Damage [Adapted from Gilbert et. al 1997] 	X						
Participant Questionnaire B	Tooth Pain/Sensitivity	PROMIS v.1.0 - Pain Intensity 3a [Modified for Dental] 	X				X		X
Participant Questionnaire B	Tooth Pain/Sensitivity	Dental Discomfort Questionnaire [Modified for Adults from Versloot et al. 2006] 	X				X		X
Participant Questionnaire B	Oral Health Quality of Life	Geriatric Oral Health Quality of Life [Atchison and Dolan, 1990] 	X				X		X
Participant Questionnaire C	Safety	Safety Questionnaire [Adapted for Adults from Milgrom et al. 2018] 			X		X		X
Participant Questionnaire D	Satisfaction	Treatment Satisfaction Questionnaire for Medication (TSQM) [Modified for Dental] 							X
Participant Questionnaire D	Satisfaction	Satisfaction with New Treatment for cavities [Modified for Adults from Crystal et al. 2017] 							X

Measure/Process	Type	Instrument/Evaluation/Procedure	Timeline (Study Week)						
			-2	0	2	26	28	52	54
Intervention Delivery	Treatment	SDF or Art + FV Based on Study Arm		X		X			
Intervention and Visit Tracking			X	X	X	X	X	X	X
Safety Questionnaire (Pre-Exam)	Safety	Safety Questionnaire [Adapted for Adults from Milgrom et al. 2018] 		X		X		X	
Dental Exam Form	Oral Health Screening	Oral Health Screening and Referral Form		X		X		X	
Dental Exam Form	Oral Health Screening	Visual Examination to Detect Gingival or Soft Tissue Stomatitis or Ulcerative Lesions [Adapted from Milgrom et al. 2018] 			X		X	X	

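### The 26-week pain and quality-of-life survey is scheduled after the second treatment, so its value mixes the effect of the first treatment with any short-term response to re-treatment

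*Combined protocol and SAP*

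**What the plan says.** - **Section 7.2 (window "Day 168 to Day 196").** The caries exam comes first. Then the hygienists "will administer the intervention treatment (based on study arm) for all previously treated lesions and newly identified active root or coronal carious lesion". The follow-up data collection block comes next: a safety call within 48 hours of treatment, then an interview in which staff "enter participant responses to the oral health symptoms, tooth pain/sensitivity, and oral health quality of life and satisfaction surveys".
- **Appendix A.** The row "SDF or Art + FV Based on Study Arm" is marked at weeks 0 and 26. The row "PROMIS v.1.0 - Pain Intensity 3a [Modified for Dental" is marked at weeks -2, 28 and 54. The Dental Discomfort (DDQ) and oral health quality-of-life (GOHRQoL) rows carry the same marks. The ICDAS exam is marked at weeks 0, 26 and 52.
- **Other places.** Section 3.2.1 states: "All primary outcomes will be measured at baseline, 26 & 52 weeks". Table 8.1.1 lists these instruments at T26. Section 8.1.1 has the pain scales given at the visit itself and quality of life within two weeks of it, without saying on which side. Section 5.4.2 states: "For all treatment visits, assessments will be conducted prior to the intervention delivery".
- **Baseline.** Section 5.3 puts the exam and treatment one to two weeks after consent and the baseline survey.
- **COVID-19.** Under the temporary procedures in section 7, the 26-week survey is done by phone when due, and exam and treatment wait for site approval. Section 4.2 reports about 40 participants without the 26-week visit or second dose.
- **Analysis.** In 11.2 the primary pain outcome is the change from baseline to one year. Section 11.4 adds a secondary repeated-measures GEE on the baseline, 26- and 52-week values with a time-by-treatment interaction. Its paragraph on heterogeneity links the longitudinal effect to the primary hypothesis.

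**The concern.** A 26-week score in a trial of six-monthly treatment is naturally read as the state of the patient at the end of the first interval. Followed as written, section 7.2 and Appendix A give something else for the patient-reported outcomes: a score taken after the second treatment. The caries-arrest score carrying the same T26 label is taken before it, so the two outcomes refer to different treatment exposures.

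The repeated-measures model then treats the 26- and 52-week surveys as two points on one time course, although one is close to a treatment and the other is far from it. Calendar time is confounded with time since last treatment. The COVID-19 procedures add a further mix, because the same nominal survey may come before the second treatment, after it, or without it. At stake are the 26-week comparison of pain and quality of life, and the time-by-treatment trend.

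**Working it through.** **1. The plan's own figure.** Section 11.2 states 89% power for the pain outcome at ICC 0.01 and 83% at ICC 0.02. Inputs from 11.2: 275 per arm, 25 per site, 15% dropout, margin 8, SD 25, one-sided alpha 0.025.

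- Mean cluster size after dropout: 25 × 0.85 = 21.25.
- Design effect: 1 + (21.25 - 1) × 0.01 = 1.2025.
- Effective n per arm: 275 × 0.85 / 1.2025 = 194.4.
- Power: Φ(8 / (25 × √(2/194.4)) - 1.96) = 88.4%.
- At ICC 0.02 the design effect is 1.405, effective n is 166.4 and power is 83.1%.

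Both stated figures reproduce. No input refers to the 26-week survey, so they do not change if it moves.

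**2. Time since treatment, from the Appendix A columns.**

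| Nominal point | Survey week | Since first treatment (week 0) | Since latest treatment |
|---|---|---|---|
| Baseline | -2 | none yet | none yet |
| 26 weeks | 28 | 28 - 0 = 28 weeks | 28 - 26 = 2 weeks |
| 52 weeks | 54 | 54 - 0 = 54 weeks | 54 - 26 = 28 weeks |

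No treatment is given at week 52. Week 28 is day 28 × 7 = 196, the last day of the 26-week window (168/7 = 24 to 196/7 = 28 weeks).

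If the survey were given in the two weeks up to the week-26 treatment, it would fall 24 to 26 weeks after the latest treatment, close to the 28 weeks at the final survey.

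**3. How firm the 2 weeks is.** Questionnaire C, the post-treatment safety survey, is also marked in column 28, yet 7.2 requires that call within 48 hours and 9.2 within 24 to 72 hours. Column 28 may therefore mean contact after the visit and not a literal week. The Contact Form is marked at week 26, while 7.2 updates contact details in the same interview as the survey. The supportable statement is after treatment, by up to about 2 weeks.

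**4. What this does to the comparison.** Let s₁ and s₂ be the mean short-term shifts in score from a recent second treatment in Arms 1 and 2, and p₁ and p₂ the shares of each arm's surveys taken after it. Then

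observed 26-week difference = difference without recent re-treatment + (p₁s₁ - p₂s₂).

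The extra term vanishes only if the two products are equal. The course within each arm shifts by p·s in any case. The documents give neither p nor s. Two features mean that equality cannot be assumed:

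- The week-26 procedure differs by arm. Section 6.11 gives Arm 2 ART at baseline and varnish at both visits. Section 7.2 has each arm's treatment given again "for all previously treated lesions and newly identified active root or coronal carious lesion". These passages must be reconciled. On either reading the Arm 2 procedure is not the Arm 1 procedure.
- Under the COVID-19 procedures p depends on site approval, and the site is the randomised unit.

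**5. Participants without a second dose.** About 40 is 40/550 = 7.3% of the original target, or 40/590 = 6.8% of the target raised by 40.

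**The case against.** The strongest reply is that this is a wording conflict touching only a secondary analysis. Much of that stands.

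- **Primary test.** A reader might infer that the non-inferiority conclusion on pain is at risk. It is not: that test uses the change to one year, and no 26-week non-inferiority test is planned. Setting an assumed shift against the margin of 8 would suggest a threat that the plan does not contain.
- **Instead of.** A reader might infer that the survey measures re-treatment and not six-month pain control. That is too strong. It also falls about 28 weeks after the first treatment, the trial compares six-monthly strategies at 12 months, and no short-term effect is quantified.
- **Section 5.4.2.** Read literally it contradicts 7.2. But it sits among sentences on the hygienists' masking and caries exams, whereas study staff collect the questionnaires. It is weak evidence about survey order.
- **Excavation.** A reader might infer that Arm 2 has just had excavation when surveyed. Sections 6.11 and 7.2 disagree, so this cannot be assumed.
- **Week 54.** The final survey also follows a visit, but no treatment is given there and no between-arm bias is shown.
- **Existing safeguard.** Section 7.5 allows the time between visits to be accounted for if necessary. It does not mention the interval from treatment to survey. The COVID-19 procedures were temporary, and nothing shows that the timing mix differed by arm.

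What the reply does not remove is the order itself. Section 7.2 and all three questionnaire rows of Appendix A place the survey after treatment, and the planned longitudinal model uses that value.

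**Conclusion.** The concern holds in a limited form. As scheduled, the 26-week PROMIS, DDQ and GOHRQoL values are taken after the second treatment, by up to about 2 weeks. The final survey falls about 28 weeks after the last treatment, and the 26-week caries exam precedes re-treatment. The 26-week patient-reported comparison and the secondary time-by-treatment GEE therefore combine the effect of the first treatment with any short-term response to the second. For COVID-19 phone surveys and the roughly 40 participants without a second dose, the mix may be different again.

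The size and direction of any shift are unknown. The between-arm difference is distorted only if the shift, or the share of surveys taken after re-treatment, differs by arm. The 12-month primary pain test and its stated power are unaffected. The conclusion assumes that sites follow 7.2 and Appendix A; a site that reads 3.2.1 or 8.1.1 as putting the survey before treatment would not produce the distortion. That ambiguity is a further reason to settle the order.

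**What to change.** 1. **26-week visits still to come.** Give Questionnaire B before the exam and treatment, on arrival or by phone in the preceding two weeks, as is done at baseline. Keep the safety survey after treatment. If the satisfaction survey is also given at 26 weeks, as 7.2 lists and Appendix A does not, it can stay there too. Align Appendix A, 7.2 and 8.1.1.
2. **Data already collected.** Use the survey dates and the treatment log to classify each 26-week survey as before, after or without second treatment. Include this class, or days since last treatment, in the repeated-measures model of 11.4 or in a sensitivity analysis. Do not report surveys taken after re-treatment as six-month durability.
3. **Week-26 treatment in Arm 2.** Reconcile 6.11 and 7.2, so that the exposure preceding the survey is known.

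The cost is one amendment and a derived variable. The form, staff and number of contacts stay the same. The exam-day visit may be slightly longer. A change made mid-trial leaves mixed survey timing across participants, which the classification variable handles. The version history for 14.0 describes recruitment as completed at the listed sites, so few 26-week visits may remain; step 2 may then matter most.

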### **7.3 52-Week Visit (T52) (Day 365 to 379)**

#### **Dental Exam and Treatment**

- Dentists *or* hygienists will administer the Safety Questionnaire (Pre-Exam).
- Hygienists will perform dental examination at participant's respective housing facility to evaluate caries arrest and new decay.
- Study staff will record results of dental examination.
- Study staff will give participants referral sheets with exam results and direction to follow up with their personal dentist for further treatment or routine dental care.

## Follow-Up Data Collection

- Study staff will contact participants by phone (within 48 hours of treatment) to complete the safety survey.
- Study staff will interview participants one-on-one at the housing facility to update contact information and enter participant responses to the oral health symptoms, tooth pain/sensitivity, oral health quality of life, *COVID-19 dental visit* and the satisfaction survey.
- Study staff will randomly select 24-30 participants who have completed treatment for three focus group sessions to be held at a housing facility during years two, *three and four*. Participants will be selected from those who have completed treatment and is geared to understanding participant experiences with non-surgical regimens and to identify ways to improve and disseminate in other community-based settings nationally.

### 7.4 Withdrawal Visit

The following procedures will be followed for participants who choose to withdraw early or whose participation is terminated by the PI:

- Personal contact (by phone or in-person) by study staff will be made to confirm withdrawal.
- Record any adverse event reported by participant.
- Debrief about the interventions.
- Obtain responses to the study questionnaires (if applicable)
- If a participant withdraws or moves from the housing facility, visits and data collection will end with these participants being considered lost to follow-up. Data collected up to the point of withdrawal will be used for analysis.

